#### 14.4.2. Intravenous Infusions (IV)

Schedules A-1 and A-2: Each IV push contains  $3 \times 10^7$  AlloStim® cells formulated in 3 ml of 1% human serum albumin in PlasmaLyteA. Pre-formulated 10 ml syringes of AlloStim® will be delivered to the study site on or prior to the IV administration day. AlloStim® is administered as an IV push over approximately 5 minutes.

Subjects may be hydrated with 500 - 2000 ml of NS (or similar) prior to infusion and may be medicated with 25-50 mg diphenhydramine PO/IV, 150 mg ranitidine (Zantac) PO or other H-2 blocker, 25-50 mg PO indomethacin (or equivalent NSAID) during or after the infusion if medically indicated.

After each IV administration of study drug, the vital signs will be monitored manually every 15 minutes or with real-time monitoring equipment for heart rate, respiration rate, blood pressure, temperature, and pulse oximetry. Values will be recorded prior, during and for 2 hours following the infusion. All changes in vital signs from baseline during and after the infusion will be recorded in the treatment notes.

The physician on duty has the authority to stop, delay, or cancel the infusion at any time if medically indicated. Any such actions that deviate from the infusion protocol will be recorded in the treatment notes and appropriate CRF or eCRF.

# 14.4.3. Intratumoral Injections (IT)

Subjects in schedule A-1 will receive an IT injection of AlloStim® (3 ml) on Day 21 into the same ablated lesion on Day 17.

Each IT injection contains either  $1 \ge 10^7$  AlloStim® cells formulated in 1 ml or  $3 \ge 10^7$  AlloStim® cells formulated in 3 ml of 1% human serum albumin in PlasmaLyteA. Preformulated 3 or 10 ml syringes of AlloStim® will be delivered to the study site on or prior to the IT administration day.

After each IT administration of study drug the vital signs will be monitored with real-time monitoring equipment for heart rate, respiration rate, blood pressure, temperature, and pulse oximetry. Values will be recorded every 15 minutes prior, during and for 2 hours following the administration. All changes in vital signs from baseline during and after the administration will be recorded in the treatment notes.

# **14.5. D**RUG ACCOUNTABILITY

As required by FDA regulations, all drug storage, procurement and usage will be carefully monitored and documented. The Principal Investigator will oversee this process and may delegate duties to others as needed to conduct the trial under Good Clinical Practices. The study site will be responsible for tracking receipt of the study drug and storage conditions of the study drug up until the time of administration. In addition, the study site must track which study drug syringe was administered to each subject, including date and time, location and route with forms and labels provided by the Sponsor.

# **14.6.** CONCOMITANT TREATMENTS PROHIBITED AND RESTRICTED THERAPIES DURING THE STUDY

No chemotherapy or other anti-cancer treatment is allowed within the first 140 days for Schedules A1-4 subjects and 105 days for Schedule B, C, D, E and F subjects ("Study Period"). If the PI determines that a subject requires anti-cancer treatment during the Study Period, the subject data will be dropped from the protocol. The safety data will be reported but will be censored as of the treatment date. An additional subject will be accrued for each censored subject.

Subjects with bone metastases may receive palliative radiation therapy to treat pain or prevent pathological fractures during the Study Period.

Subjects experiencing anemia can be transfused as medically required (e.g., if Hgb < 9.0) at discretion of the PI. Erythropoietin may be used in continuation therapy, if indicated.

Subjects will receive medically appropriate supportive care, including treatment of pain and infection during the Study Period.

Additional IV booster infusions are allowed at the discretion of the investigator on a monthly basis after the completion of the Study Period.

Use of steroids is not allowed unless medically indicated. NSAIDs should be used as first choice and methylprednisone or SoluMedrol as next choice if anti-inflammatory medication

is deemed necessary. Inhaled steroids are allowed on study. If a subject is administered systemic steroids during the Study Period for any reason, the subject will be dropped from the study and the data will be censored from the first day of steroid administration.

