## **Brief Description of the Protocol:**

This is a single center, open label study comparing CryoVaxTM personalized anti-tumor vaccine protocol combining the cryoablation of a selected metastatic lesion with intra-lesional immunotherapy with AlloStim® alone. The treatment schedules both have the following steps: (1) priming with intradermal AlloStim®; (2) vaccination combining cryoablation with intratumoral AlloStim® or intravenous AlloStim® dosing in the place of cryoablation; (3) activation with intravenous AlloStim®; and (4) booster with intravenous AlloStim®. All subjects are followed for safety during the dosing period and until 28 days following the last dose (Safety Evaluation Period"). All subjects are continued to be followed for survival after the Safety Evaluation Period.

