However, due to the marginal survival benefit and high toxicity of Regorafenib , the NCCN guidelines also state that physicians can consider to enroll KRAS mutant patients who progress on FOLFOX and FOLFIRI with bevacizumab and maintain adequate performance status and end-organ function into clinical trials, including phase I trials [41]. The EMA European Public Assessment Report (EPAR) for Regorafenib states that the drug is indicated in adult patients with metastatic colorectal cancer who have been previously treated with or are not considered candidates for other available therapies, including patients with KRAS mutant tumors, though physicians are recommended to carefully evaluate benefits and risks when prescribing Regorafenib in patients with KRAS mutant tumors.

Although Regorafenib is a recommended therapy for metastatic colorectal cancer after failure of standard therapies, it is important to note that it comes at a starting cost of \$9,350 per 28-day cycle. A recent editorial questions the cost-effectiveness of Regorafenib therapy. The authors comment on the small incremental survival benefit, short PFS, and the potentially substantial adverse effects. They suggest that identification of the subset of patients most likely to derive significant clinical benefit from Regorafenib therapy become a high priority [42].

This protocol does not require prior Regorafenib for eligibility. This is based on the subset analysis of the CORRECT trial demonstrating little OS benefit for the KRAS mutant subset of patients and is consistent with NCCN guidelines recommending consideration of clinical trial options for third-line KRAS mutant mCRC. Subjects in this protocol that are progressing or not responding to experimental therapy can add Regorafenib after the Safety Evaluation Period as salvage therapy.

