The median progression-free survival was 2.0 months in the TAS-102 group and 1.7 months in the placebo group. 221 patients (44 percent) in the TAS-102 group and 42 patients (16 percent) in the placebo group had achieved disease control (complete response, partial response, or stable disease) measured at least 6 weeks after the patients were randomly assigned to treatment groups. In addition, the time to worsening of performance status was significantly longer in the TAS-102 group than in the placebo group (5.7 versus 4.0 months). Patients in the TAS-102 group experienced few serious adverse events. Overall, adverse events of grade 3 or higher occurred more frequently in the TAS-102 group than in the placebo group (69 percent versus 52 percent). The most common adverse events associated with TAS-102 included neutropenia, which occurred in 38 percent of those treated, and leukopenia, which occurred in 21 percent. Four percent of the patients in the TAS-102 group developed febrile neutropenia, and there was one death related to TAS-102 [43].

Based upon review of data submitted, the NCCN decided (in a Web Conference on July 24, 2015) to add to the NCCN-Guidelines V.1.2016 the regimen of trifluridine + tipiracil as a subsequent therapy option for patients with disease progression after oxaliplatin- and irinotecan-based chemotherapy.

This protocol does not require prior TAS-102 for eligibility. This is based on the minimal efficacy of TAS 102 in the subject population. A reported phase II trial of TAS-102 found an overall survival benefit in Japanese patients with metastatic colorectal cancer refractory to treatment. The RECOURSE study was a global phase III trial conducted in 13 countries. Patients had metastatic colorectal cancer refractory to all standard therapies including with wild-type KRAS tumors. Patients were treated with TAS-102 (534 patients) or placebo (266 patients) and directly compared. The researchers found that TAS-102 prolonged overall survival experiencing a median overall survival of 7.1 months for TAS-102 and 5.3 months for placebo, a 1.8 month increase.

Subjects in this protocol that are progressing or not responding to experimental therapy can add TAS-102 after the Safety Evaluation Period as salvage therapy.

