#### **16.1.6. Exploratory Endpoints**

All data will be summarized using descriptive statistics by dosing schedule. All subjects who received any study medication will be included in the analysis.

If the subject is alive at the end of the follow-up period or is lost to follow-up, OS will be censored on the last date the subject is known to be alive.

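### Section 14.6 drops and replaces A-1 and A-2 subjects who need anti-cancer treatment in the first 140 days, although section 6.2 permits salvage 28 or 35 days earlier with full dosing and 16.1.6 analyses every treated subject

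*Combined protocol and SAP*

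**What the plan says.** Section 14.6 defines a Study Period for the current schedules: "No chemotherapy or other anti-cancer treatment is allowed within the first 140 days for Schedules A1-4 subjects". Palliative radiation for bone metastases is exempt. If the investigator decides that anti-cancer treatment is required in that period, three things follow:

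- For the data as a whole, 14.6 says that "the subject data will be dropped from the protocol".
- For safety, it makes a partial exception: "The safety data will be reported but will be censored as of the treatment date".
- For numbers, it provides for replacement: "An additional subject will be accrued for each censored subject".

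The background sections set a different limit. Subjects who are progressing or not responding "can add Regorafenib after the Safety Evaluation Period as salvage therapy" (section 6.2.7), and they "can add TAS-102 after the Safety Evaluation Period as salvage therapy" (section 6.2.1, TAS-102). The Protocol Abstract (Brief Description) defines the end of that period: "All subjects are followed for safety during the dosing period and until 28 days following the last dose".

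For the exploratory endpoints, which include OS, section 16.1.6 says: "All subjects who received any study medication will be included in the analysis". It censors OS for subjects alive at the end of follow-up or lost to follow-up. Section 8 continues efficacy evaluation monthly for each subject until the subject dies or is lost.

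**The concern.** The two limits differ, and the protocol does not say which one governs. A subject who starts regorafenib or TAS-102 when section 6.2 first allows it is still inside the 140 days of 14.6. That subject is then exposed to being dropped and replaced for doing something the protocol permits.

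The trigger depends on outcome, because the subjects who start salvage are mainly those who are progressing. The second primary objective in section 7.1 is to find the schedule with the best efficacy and the fewest adverse events. Section 8 picks the Part 2 schedule on safety and efficacy data from three subjects per schedule. A rule that takes out progressors and puts new subjects in their place can make a schedule look better than it is, and with three subjects one replacement is a large change.

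The window is also one in which salvage is likely to be considered. Day 91 is the only CT scheduled after baseline (Protocol Abstract, Radiology Assessment; section 11.2.4), and with full dosing section 6.2 opens the way to salvage soon after it.

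**Working it through.** **Inputs.**
- Treatment-free period: 140 days (14.6). Its origin is not stated; Day 0 is assumed.
- Safety Evaluation Period: ends 28 days after the last dose (Protocol Abstract).
- Last dated dose: Day 84 in A-1 and Day 77 in A-2 (section 8).
- Permitted delay: up to 7 days for a missed appointment (12.1).

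The plan does not derive the 140 days, so there is no figure to reproduce. It would equal last dose + 28 only with a last dose on Day 140 − 28 = Day 112, which neither schedule has.

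**Gap between the limits.** Gap = 140 − (last dose + 28).

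| Case | A-1 | A-2 |
|---|---|---|
| All dated doses on time | 140 − (84 + 28) = 28 | 140 − (77 + 28) = 35 |
| Last booster 7 days late | 140 − (91 + 28) = 21 | 140 − (84 + 28) = 28 |
| First booster only | 140 − (56 + 28) = 56 | 140 − (49 + 28) = 63 |
| No boosters (last dose Day 28) | 140 − (28 + 28) = 84 | 84 |

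If the 140 days ran from Day −14 (start of baseline), they would end on Day 126. The full-dosing gaps would then be 126 − 112 = 14 and 126 − 105 = 21 days. The Abstract mentions three A-2 boosters but dates only two. If a third were given on Day 105 (assumed, same 28-day spacing), the period would end on Day 133. The gap would be 7 days from Day 0, and there would be none from Day −14.

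**Position of the Day 91 CT.** With full dosing, the Safety Evaluation Period ends 112 − 91 = 21 days (A-1) or 105 − 91 = 14 days (A-2) after the CT. With the one-week CT window in 12.1 these become 14 to 28 and 7 to 21 days, so the CT still comes first. For early stoppers the order reverses. Permitted salvage can precede Day 91 by 91 − 84 = 7 days (A-1, last dose Day 56), 91 − 77 = 14 days (A-2, last dose Day 49) or 91 − 56 = 35 days (last dose Day 28).

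**What dropping does, under each reading.**
- *Removal.* Take a schedule with one progressor among three subjects. Observed non-progression is 2/3. If the progressor is removed and replaced by a non-progressor, it becomes 3/3.
- *Censoring at the treatment date.* With full dosing the Day 91 results stay and the count remains 2/3. OS is then censored at a time chosen because the subject is doing badly, so the censoring is informative.

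**How often.** The documents give no rate of salvage starts in the window. If each subject has probability p (assumed), the chance that at least one of n is affected is 1 − (1 − p)^n.

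| p (assumed) | n = 3 (one schedule) | n = 6 (Part 1) |
|---|---|---|
| 10% | 27% | 47% |
| 20% | 49% | 74% |
| 30% | 66% | 88% |

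**Safety.** The window opens after the Safety Evaluation Period ends, and 16.1.3 leaves later adverse events out of the safety evaluation. Censoring safety data in this window therefore changes nothing in the primary analysis.

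**The case against.** **The two rules can be read together.** Section 6.2 allows salvage after the Safety Evaluation Period without naming its first day, so a start after Day 140 satisfies both texts. Section 13.2 has subjects treated as clinically indicated once study therapy ends, so clinical permission and data consequence could be separate matters. This stands in part: no patient is denied treatment. But the permission in 6.2 carries no later limit, and 14.6 is triggered when the investigator judges treatment to be required, so waiting may not avoid the drop.

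**Dropping may mean censoring.** Section 14.6 itself refers to these subjects as censored, and its steroid rule pairs leaving the study with censoring from a date. This stands. A reader might infer that 14.6 necessarily deletes the subject, and the text does not settle that. The 2/3 to 3/3 example holds only under removal.

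**16.1.6 does not list every censoring reason.** A reader might infer that any further reason contradicts it. The documents do not support that. Censoring also follows withdrawal of consent (Abstract, Statistical Analysis), repeated or out-of-window treatment deviations (12.1), immunosuppressive agents (14.6) and steroids (16.1). The conflict with 16.1.6 is about keeping all treated subjects in the analysis, and it is sharp only if dropping means removal.

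**The longer period may be deliberate.** A reader might infer that 140 days is a remnant of deleted schedules. It matches neither current schedule, but 14.6 names A-1 and A-2 within its range. The protocol also expects late responses to immunotherapy, so a longer treatment-free period could be intended.

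**The consequence may be limited.** OS and RECIST are exploratory, the comparison is not randomised, and the date of the Part 2 decision is not given. Section 8 closes enrolment once all cohorts finish the Safety Evaluation Period, so a late replacement might not be possible. All of this limits the effect, but none of it makes an outcome-dependent replacement rule sound.

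**Conclusion.** The point holds. With on-time full dosing, sections 14.6 and 6.2 disagree for 28 days in A-1 and 35 days in A-2, counting from an assumed Day 0. Counting from Day −14 reduces this to 14 and 21 days. The gap closes only if a third A-2 booster on an assumed Day 105 is combined with the Day −14 origin. Subjects who take permitted salvage in the window are to be dropped and replaced under 14.6, while 16.1.6 keeps every treated subject and section 8 follows each one.

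The harm depends on what dropping means. Removal selectively replaces progressors in the three-per-schedule data behind the Part 2 choice. Censoring keeps the Day 91 results with full dosing but makes OS censoring informative. Neither gives a fair basis for judging efficacy.

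A reader might also infer that the primary safety result is compromised, or that every anti-cancer treatment triggers the rule. The documents support neither: safety is unaffected in this window, and palliative bone radiation is exempt. The probabilities of an affected subject rest on assumed rates, and the inconsistency does not depend on them.

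**What to change.** 1. In 14.6, state that starting anti-cancer therapy does not remove a treated subject's data from the efficacy and survival summaries, and that the subject is not replaced in them.
2. Follow OS to death under 16.1.6. Present OS censored at the start of salvage as a sensitivity analysis.
3. Record the agent and start date of salvage at the survival calls already planned (Protocol Abstract, Survival).
4. Flag any Day 91 CT or biopsy done after salvage has started.
5. Use one stated date for A-1 and A-2 in both 14.6 and 6.2, and delete the references to removed schedules.

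Whether that date is the end of the Safety Evaluation Period or Day 140 is the sponsor's choice, and it is a trade-off. With the first, a subject whose last dose was on Day 28 could start salvage after Day 56 and still contribute a Day 91 result, which is why the flag is needed. With the second, the permissions in 6.2 have to move to Day 140.

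The cost is one CRF field, one flag, one sensitivity summary and the ethics approval that any amendment needs (17.4). It adds no visits. The main downside is that OS will include any effect of salvage therapy, which the sensitivity analysis helps to show.

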#### Dexamethasone therapy is contraindicated in immunotherapy protocols, as it has been shown to selectively cause apoptosis of activated effector immune cells.

Administration of dexamethasone will necessitate dropping the subject from the protocol and censoring data from the first day of administration.

If evidence of severe immune-related adverse events (e.g., GVHD, VOD, autoimmune disease) at any time during the protocol, the investigator should first attempt to suppress the inflammation using high dose IV SoluMedrol.

If the condition is refractory to steroids, additional immunosuppressive agents should be considered (e.g., Imuran, cyclosporine). Specific agents for cytokine storm related events, such as Remicade can be considered. T-cell inflammation can be treated with Orthoclone OKT3, monocyte inflammation with Etoposide and B-Cell inflammation with Rituximab. If immunosuppressive treatment does not reverse a suspected immune-mediated adverse event, dexamethasone should be administered to eliminate any activated immune cells. Dexamethasone can be administered alone or in combination with Cytoxan as a reversal strategy.

All concurrent medical care must be documented. Any use of immunosuppressive agents will result in censor of the subject for analysis, but the AE/SAE must be reported even after administration and documented.

#### **15. ADVERSE EVENTS**

An adverse event (AE) is any untoward medical occurrence in a trial subject that has been administered the study drug; the event does not necessarily have to have a causal relationship with AlloStim® treatment or usage.

All observed or volunteered AEs, regardless of causal relationship to the investigational product, will be recorded as an adverse event on a supplied case report form (CRF) or electronic CRF (eCRF). Events involving adverse drug reactions, illnesses with onset during the study, or exacerbations of preexisting illnesses should also be recorded as AEs.

Exacerbation of pre-existing illness, including the disease under study, is defined as manifestation (sign or symptom) of the illness that indicates a significant increase in the severity of the illness as compared to the severity noted at the start of the trial and the known normal course of disease progression for stage IV colorectal cancer. This may include worsening or increase in severity of signs or symptoms of the illness, increase in frequency of signs and symptoms of an intermittent illness, or the appearance of new manifestations/complications. Exacerbation of a pre-existing illness should be considered when a subject requires new or additional concomitant drug or non-drug therapy for the treatment of that illness during the trial.

Lack of, or insufficient clinical response, benefit, efficacy or therapeutic effect, should not be recorded as an AE. The investigator must make the distinction between exacerbation of preexisting illness and lack of therapeutic efficacy. The investigator can take into consideration the results of radiology and pathology exams and immunological monitoring data when making this assessment.

In addition, abnormal objective diagnostic procedures findings (e.g., abnormal laboratory test results) should be recorded as an AE if it is fulfills one or more of the following:

- Results in subject's withdrawal by the Investigator;
- Is associated with an SAE;
- Is associated with clinical signs or symptoms;
- Is considered by the physician to be of clinical significance;
- Requires the subject to have study therapy discontinued, modified, or interrupted;
- Requires the subject to receive specific corrective therapy; and
- Requires diagnostic evaluation to assess the risk to the subject.

Laboratory adverse events should be captured on the AE /SAE CRF/eCRF as appropriate. It is expected that wherever possible, the clinical, rather than the laboratory term, will be used by the reporting investigator.

Clinically significant changes in physical examination findings should also be recorded as AEs.

#### **15.1.1.** Clinical Laboratory Adverse Events

All laboratory test values captured as part of the study should be recorded on the appropriate laboratory test results pages of the CRF/eCRF. In addition, to collecting additional information about clinically important laboratory abnormalities, at a minimum, the following laboratory abnormalities should be captured on the AE /SAE CRF/eCRF as appropriate:

- Any laboratory test result that meets the criteria for an AE or SAE;
- Any laboratory abnormality that requires the subject to have study therapy discontinued, modified, or interrupted; and
- Any laboratory abnormality that requires the subject to receive specific corrective therapy.

It is expected that wherever possible, the clinical, rather than the laboratory term, will be used by the reporting investigator.

